## LIST OF ABBREVIATIONS AND RELEVANT DEFINITIONS

AE	Adverse Event
AESI	Adverse Event of Special Interest
ALAT	Alanine aminotransferase
ASAT	Aspartate aminotransferase
CBG	College ter Beoordeling van Geneesmiddelen
CBS	Centraal Bureau voor de Statistiek
CI	Confidence Interval
COVID-19	Coronavirus Disease 2019
CRP	C-reactive protein
CTCAE	Common Terminology Criteria for Adverse Events
DSMB	Data Safety Monitoring Board
ECOG PS	Eastern Cooperative Oncology Group Performance Status
EMA	European Medicines Agency
EU	European Union
GBA	Gemeentelijke Basis Administratie
GCP	Good Clinical Practice
GMC	Geometric Mean Concentration
IC	Informed Consent
ICI	Immune Checkpoint Inhibitor
IKNL	Integraal Kankercentrum Nederland
IFN-ɣ	Interferon-gamma
irAE	immune related Adverse Event
IST	Investigator Sponsored Trial
METC	Medical research ethics committee (MREC); in Dutch: medisch-ethische
	toetsingscommissie (METC)
MIA	Multiplex Immunoassay
NIBSC	National Institute for Biological Standards and Control
PBMC	Peripheral Blood Mononuclear Cells
PD1	Programmed Death 1 (immune checkpoint)
PD-L1	Programmed Death-ligand 1 (immune checkpoint)
PIF	Participant Information Form
(S)AE	(Serious) Adverse Event
SARS-	Severe Acute Respiratory Syndrome Coronavirus 2
CoV-2	
SPC	Summary of Product Characteristics; in Dutch: officiële productinformatie

IB1-tekst

- Sponsor The sponsor is the party that commissions the organisation or performance of the research, for example a pharmaceutical company, academic hospital, scientific organisation or investigator. A party that provides funding for a study but does not commission it is not regarded as the sponsor, but referred to as a subsidising party.
- SUSAR Suspected Unexpected Serious Adverse Reaction
- WHO World Health Organization
- WMO Medical Research Involving Human Subjects Act; in Dutch: Wet Medischwetenschappelijk Onderzoek met Mensen

#### SUMMARY

**Rationale:** Patients with cancer have an increased risk of adverse outcome of COVID-19, which is determined by their underlying disease and/or cancer treatment. Therefore, vaccination of cancer patients against COVID-19 is recommended. However, phase III studies do not provide robust information on efficacy and safety in this vulnerable population. In patients with cancer, the disease itself, but also immunotherapy and chemotherapy, may have a significant impact on the ability to develop an effective immune response to COVID-19 vaccination, and could even increase the risk of adverse events.

**Objective**: To assess immune response and adverse events after administration of one approved vaccine against COVID-19 in patients with cancer treated with immunotherapy and/or chemotherapy.

**Study design:** This is a prospective multicenter, multicohort study.

Study population: Four cohorts will receive vaccination against COVID-19:

- A. Individuals without cancer (N=246, i.e., partners of patients in cohort B, C, and D)
- B. Patients with cancer treated with immunotherapy (N=135)
- C. Patients with cancer treated with chemotherapy (N=246)
- D. Patients with cancer treated with chemo-immunotherapy (N=246)

Main inclusion criteria:

- age of 18 years or older
- life expectancy > 12 months
- ability to provide informed consent
- last immunotherapy cycle within 3 months of vaccination (cohort B and D)
- last chemotherapy cycle within 4 weeks of vaccination (cohort C and D) Main exclusion criteria:
- confirmed SARS-CoV-2 infection (current or previous)
- women who are pregnant or breastfeeding
- active hematologic malignancy
- immune deficiency not related to cancer or cancer treatment
- systemic treatment with immune suppressive medication, including chronic steroid use of
- >10 mg prednisone or equivalent

**Intervention**: Participants will be vaccinated against COVID-19 with an approved vaccine. Blood will be drawn at different time points by venipuncture and mucosal lining fluid will be collected at 2 time points.

**Main study parameters/endpoints:** The primary endpoint is the antibody based immune response on day 28 after the second vaccination. Participants will be classified as responders or non-responders. The definition of response is seroconversion defined as presence of SARS-CoV-2 spike S1-specific IgG antibodies in individuals without measurable anti-S antibodies at baseline. Participants who are seropositive at baseline will not be included in the analysis of the primary endpoint. The percentage of responders of each patient cohort will be compared with the percentage responders in the control group. Safety is a secondary endpoint which will be reported in terms of percentage of solicited local and systemic adverse events (AEs) graded according to severity. Other secondary endpoints include longevity at 6 months and levels of SARS-CoV-2 specific T cell responses.

Nature and extent of the burden and risks associated with participation, benefit and group relatedness: Participants will have to visit the hospital at 6 time points, and participants who receive a third vaccination will have 2 additional hospital visits. The vaccine will be administered two times according to the standard of care, with the option of a third vaccination for participants without an adequate response after 2 vaccinations. Blood will be drawn (~373 ml in total for participants receiving 2 vaccinations, and ~539 ml in participants receiving 3 vaccinations) prior to the vaccinations and at day 28 and 6 months, 11 months and 18 months after the second vaccination. Nasal mucosal lining fluid samples will be collected at baseline and day 28 after the second vaccination in a subgroup of patients. Blood sampling will give minor discomfort, mucosal lining fluid collection is a non-invasive procedure. Vaccination can cause AEs including fatigue, chills, headache, myalgia, and pain at the injection site. For seven days after each vaccination, participants will be asked to record local and systemic reactions using a questionnaire. At baseline and at 3, 6, 9,12, 15 and 18 months after the second vaccination, patients will be asked to complete questionnaires about potential subsequent testing for SARS-CoV-2, diagnosis of COVID-19, and severity of COVID-19.

This study will collect information on immune response and adverse events after vaccination against COVID-19 in a vulnerable patient cohort. It will also explore immune response and safety of a third vaccination in participants without an adequate antibody response after the second vaccination. Understanding the ability or disability to mount a protective immune response after vaccination will help to counsel patients during the pandemic and support

decisions on whom to vaccinate and to identify patients who require other measures to protect them from COVID-19. Participants will be informed about their antibody titer in a letter that includes an explanation about what this means to them. This will be done after antibody measurements have been completed for day 28 after second vaccination, and again after completion of measurements for 6 months and 28 days after third vaccination, and 11 months and 18 months after the second vaccination.

## 1. INTRODUCTION AND RATIONALE

#### 1.1 Impact of COVID-19 pandemic on oncological care

The SARS-CoV-2 pandemic is having a huge impact on societies all around the globe. As of December 8, 2020, over 65 million people have been diagnosed with Coronavirus induced disease (COVID-19), resulting in over 1,5 million deaths with numbers still increasing [1,2]. Over the past 6 months, regular health care, including cancer care [3,4], has been scaled down because hospitals were flooded with patients with COVID-19. In addition, hospital visits for anticancer therapies may put patients at even more risk of getting infected with SARS-CoV-2 [5,6]. As the COVID-19 pandemic overwhelmed healthcare systems worldwide, nonevidence-based decisions had to be made about the treatment of patients with cancer. Consequently, oncological treatment was frequently adjusted during the COVID-19 pandemic, even in regions with relatively low COVID-19 incidence [3]. These treatment adjustments were made according to COVID-19 guidelines of (inter)national oncological societies, which were primarily based on expert opinions [7-10]. The limited capacity to deliver cancer care, the lockdown isolating patients at home, and their fear of entering hospitals, has led to suboptimal cancer care. In addition, there was a 30% underdiagnosis and delayed diagnosis of cancer in the Netherlands [11,12]. This most likely will result in higher cancer-specific mortality rates in the years to come.

#### 1.2 Outcome of COVID-19 in patients with cancer

Patients with cancer have a higher risk for a dismal outcome of COVID-19 [13-15]. Therefore, international registries have been initiated to identify the clinical characteristics of cancer patients with severe COVID-19 [5,6, 16-25]. The worse outcome of COVID-19 in patients with cancer is determined by their underlying disease and/or cancer treatment. In particular, lung cancer and hematological malignancies are independent risk factors for a fatal outcome of COVID-19 [4]. In addition, chemotherapy and chemo-immunotherapy have been identified as risk factors for mortality of COVID-19 in patients with cancer [26,27].

#### 1.3 COVID-19 vaccination

Several vaccines are currently in development and the RNA vaccines by BioNTech/Pfizer and Moderna [28-31], were granted conditional marketing authorization by EMA. Vaccination of the Dutch population has started in January 2021. For the VOICE study the mRNA-1273 SARS-CoV-2 vaccine from Moderna will be used. In the randomized phase III study with mRNA-1273, 30,420 volunteers received two intramuscular injections of the vaccine (100 ug) or placebo 28 days apart [32]. None of the participants was treated with chemotherapy and/or immunotherapy for cancer at the time of vaccination. In the placebo group 185 participants developed symptomatic COVID-19 versus 11 participants who received the vaccine, resulting in 94.1% vaccine efficacy (95% CI, 89.3 to 96.8%; P<0.001). Severe COVID-19 only occurred in the placebo group: in 30 participants including one fatality. Solicited AEs at the injection site were common in the vaccine group (84.2% after the first injection and 88.6% after the second injection) but mainly low grade and of short duration. Solicited systemic AEs in this group were reported by 54.9% of the participants after the first dose and by 79.4% after the second dose, and mainly consisted of headache, fatigue, myalgia and chills. The rate of unsolicited AEs and SAEs up to 28 days after vaccination was similar in both arms. Hypersensitivity reactions occurred in 1.5% in the vaccine group and 1.1% in the placebo group.

#### 1.4 COVID-19 vaccination in patients with cancer

Patients with cancer have an increased risk for an adverse outcome of COVID-19 [13-15]. As a consequence, many patients strictly adhere to self-isolation, resulting in loneliness and loss of quality of life. Therefore, vaccination needs to be prioritized for these vulnerable patients. In addition, effective COVID-19 vaccination is of extreme importance to protect patients with cancer to continue care and cure. An immune response to vaccination would not only protect them from life-threatening COVID-19 but also allow close contact with their loved ones. Therefore, patients and patient organizations have already claimed prioritization of vaccination against COVID-19 for patients with cancer.

For proper protection against COVID-19 by vaccination, specific immune responses need to be induced. SARS-CoV-2 specific immune cells are essential to combat the virus. B cells are important for antibody responses to neutralize the virus, while CD8 positive T cells can specifically recognize and eradicate virus-infected cells. In addition, CD4 positive T cells are required for providing necessary help to B cells and CD8 positive T cells. Cancer immunotherapy activates T cells against cancer cells by blocking the interaction between Programmed Death 1 (PD1) and its ligand (PD-L1) [33]. How this treatment impacts immune responses to vaccination is unknown. Chemotherapy causes bone marrow suppression and reduces the number of immune cells in the blood circulation, which may hamper the induction of protective immune responses after vaccination as suggested in studies on

influenza vaccination [34]. However, it is striking how little information is available on safety and efficacy of vaccination in cancer patients. As compared to the healthy population, patients with cancer treated with immunotherapy and/or chemotherapy may be more prone to adverse events of vaccination. Immunotherapy could potentially result in an augmented immune response to vaccination resulting in fever, chills, and other immune-related adverse events. Chemotherapy is known for significant fatigue, which impacts performance status and increases vulnerability. As a result, immunotherapy and chemotherapy may have a significant impact on the effectiveness but also on the safety of COVID-19 vaccination. In several countries including Belgium and France, immunocompromised patients are now offered a third vaccination. An advice from the Dutch Health Council about additional vaccination of immunocompromised patients in the Netherlands is expected soon. To protect patients with cancer from COVID-19, clinical trials are urgently needed to evaluate whether they develop an effective, safe, and durable immune response during immunotherapy and/or chemotherapy.

#### 1.5 Current trial

The one central question is whether patients with cancer and especially those requiring systemic treatment, can develop protective immunity against COVID-19 upon vaccination. This question needs to be answered urgently and would help the medical oncology community to decide whether optimal cancer care can be delivered safely to vaccinated patients with cancer. In the VOICE trial, this important question will be addressed in a longitudinal cohort in which patients with solid cancers requiring systemic therapy will be vaccinated with the available COVID-19 vaccine according to the Dutch vaccination program. Patients with hematologic malignancies are not included in this study because it is known from influenza vaccination studies that those patients are frequently not able to build an effective immune response [35]. This means that protection of patients with a hematologic malignancy may require a different protective strategy such as treatment with SARS-CoV-2 specific antibodies.

In the VOICE study, the ability to mount antibody responses, will be measured in three cohorts of patients treated with chemotherapy, immunotherapy, or chemo-immunotherapy. Their immune response to COVID-19 vaccination will be compared to the immune response of participants without cancer and vaccinated with the same vaccine. Next to measuring antibody responses and their kinetics over time, also an in-depth analysis of T cell immunity, side effects of vaccination, SARS-CoV-2 infection rate, and severity of COVID-19 will be assessed. The VOICE trial will address a high unmet medical need, i.e., vastly gathering information on vaccine safety and effectiveness in one of the most vulnerable populations and could serve as a model for studies in other fragile populations. Understanding the ability

or disability to mount a protective immune response to a COVID-19 vaccine will help to counsel patients with cancer during this pandemic. Moreover, it will support decisions how to administer the best cancer care safely.

## **1.6 First results VOICE trial**

Between February 17th and March 12th, 2021, 791 participants were enrolled in the current trial. For the primary endpoint at 28 days after the second vaccination, 743 participants were evaluable (per-protocol population): 240 individuals without cancer and 131 patients receiving immunotherapy, 229 patients receiving chemotherapy, and 143 patients receiving chemo-immunotherapy. SARS-CoV-2-binding antibody response (>10 binding antibody units (BAU)/mL) was found in 100%, 99.3%, 97.4%, and 100% of the participants in cohorts A, B, C, and D, respectively.

Given the importance for clinical decisions, we defined, based on neutralizing capacity, a cutoff level at 300 BAU/mL to discriminate between suboptimal and adequate responders. Twenty eight days after the second vaccination, 99.6% (A), 93.1% (B), 83.8% (C), and 88.8% (D) had an adequate response. Spike-specific T cell responses were detected in almost half of the suboptimal and non-responders. No new safety signals were observed [36].

#### 1.7 Third vaccination

Although most patients with solid tumors develop an adequate SARS-CoV-2-binding antibody response after vaccination, 6.9%, 16.2%, and 11.2% of patients treated with immunotherapy, chemotherapy, and chemo-immunotherapy, respectively, are still suboptimal or non-responders. As most of them show an increase in antibody concentration after the second vaccination, an additional third vaccination might turn them into adequate responders. In the extension of the VOICE trial, we will investigate whether non and suboptimal responders might benefit from a third vaccination. We will study whether an additional mRNA-1273 administration can improve the antibody response of participants in the VOICE trial who had a low antibody response on day 28 following two mRNA-1273 vaccinations. In addition safety, neutralizing antibodies and SARS-CoV-2 Spike-specific interferon-gamma T cell response will be studied.

# 1.8 Current vaccination strategy in the Netherlands

Since October 2021, all patients with cancer who received chemotherapy and/or immunotherapy during or within 3 months before their first vaccination received an invitation for a third vaccination with an mRNA vaccine as part of their primary vaccination. This applies to all patients in the VOICE trial who did not receive a third vaccination within the study. Furthermore, everyone is entitled to receive a booster vaccination with an mRNA vaccine at least 3 months after completion of the primary vaccination, whether that consisted

of 2 or 3 vaccinations. This means that the majority of the study participants will have had extra vaccinations at different time points by January 2022. Therefore, we will implement 2 cross sectional measurements at 11 and 18 months after the second vaccination (in February and September 2022) and record the date and type of those extra vaccinations retrospectively. This will provide insight in the immune status against COVID-19 of cancer patients in the Netherlands compared to a cohort without cancer in 2022.

# 2. OBJECTIVES

Primary Objective:

 To assess the antibody based immune response after vaccination against COVID-19 in patients with cancer treated with immunotherapy and/or chemotherapy as compared to controls

Secondary Objectives:

- To assess adverse events (AEs) after vaccination against COVID-19 in patients with cancer treated with immunotherapy and/or chemotherapy
- To assess durability of the antibody response in patients with cancer treated with immunotherapy and/or chemotherapy
- To analyze the SARS-CoV-2 specific T cell response after vaccination in patients with cancer treated with immunotherapy and/or chemotherapy

Exploratory Objectives:

- To perform in-depth analysis of cellular immune responses in patients with cancer treated with immunotherapy and/or chemotherapy
- To identify baseline (immune) parameters associated with vaccination response in patients with cancer treated with immunotherapy and/or chemotherapy
- To assess the neutralizing capacity of antibodies against SARS-CoV-2 after vaccination in patients with cancer treated with immunotherapy and/or chemotherapy
- To analyze induction of mucosal antibodies against SARS-CoV-2 in mucosal lining fluid samples. To describe the incidence of SARS-CoV-2 infection, outcome of COVID-19 during 12 months after vaccination in patients with cancer treated with immunotherapy and/or chemotherapy
- To analyze SARS-CoV-2-binding antibody concentration after a third vaccination in participants without an adequate antibody response after two vaccinations
- To analyze safety of a third vaccination

#### 3. STUDY DESIGN

This is a prospective multicenter cohort study, designed to evaluate the immune response and safety after vaccination against COVID-19 in three cohorts with cancer patients and one cohort of participants without cancer (see Fig.1). The patient cohorts are defined by type of cancer treatment. Immunotherapy, chemotherapy and chemo-immunotherapy were chosen because these treatment regimens may affect the efficacy and safety of vaccination against COVID-19 in different ways.

Figure 1. Trial design

To reflect the real-world population of patients with cancer treated with immunotherapy and/or chemotherapy, this trial is designed as inclusive as possible. Exclusion criteria are minimal and serve to exclude patients who are not evaluable, or in whom vaccination is considered not safe or not effective. A cohort of volunteers without a cancer diagnosis is included for comparison. Because age is an important predictor of the ability to mount an effective immune response to vaccination [37], partners of patients are enrolled in cohort A. We will take care that from all patient cohorts partners are approached, until cohort A is complete. We anticipate that accrual of cohort A will be completed earlier than the patient cohorts.

All participants will receive two vaccinations against COVID-19 according to standard of care. Participants with an inadequate antibody response will be offered a third vaccination. To assess immune responses after vaccination, blood samples will be collected at baseline (i.e. prior to first vaccination), at the day of the second (and if applicable the third) vaccination and at day 28 after the second and third vaccination and 6, 11 and 18 months after the second vaccination by venipuncture. To evaluate hematology, with or without liver and kidney function, additional blood samples will be collected at baseline, at the day of the second and third vaccination, and at day 28 after the second and third vaccination and 6, 11 and 18 months after the second vaccination. Nasal mucosal lining fluid will be collected at baseline and at day 28 after the second vaccination according to a non-invasive sampling method.

To evaluate vaccination related AEs, patients will be asked to collect solicited local and systemic AEs for 7 days after each vaccination using a questionnaire. Similarly serious AEs (SAEs) will be collected for 7 days after each vaccination. Most patients who receive systemic cancer treatment experience multiple AEs that are cancer treatment related, or disease related. As vaccination related AEs are mainly expected within the first week after vaccination, it is not useful to collect all AEs for a prolonged period. Instead, all newly occurring immune related AEs (irAEs) are collected for the immunotherapy and chemo-immunotherapy cohorts (B and D) up to 28 days after the second and if applicable the third vaccination. irAEs are toxicities from immune checkpoint inhibitors and do not include infusion reactions [38]. Furthermore, adverse events of special interest (AESIs) will be collected for the duration of the study in the patient cohorts.

Information on incidence of SARS-CoV-2 infection, outcome of COVID-19 during 18 months after the second vaccination will be collected using questionnaires. For the study participants who give separate consent, information on positive corona tests during the study will also be collected from the RIVM.

Although this study is not powered to detect differences in protection against COVID-19 between patients and controls, information on incidence of SARS-CoV-2 infection, outcome of COVID-19 will be collected up to 18 months after the second vaccination for descriptive purposes.

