# 4. STUDY POPULATION

# 4.1 Population (base)

# 4.2 Inclusion criteria

To be eligible to participate in this study, a subject must meet all of the following criteria:

- Age of 18 years or older
- Life expectancy > 12 months
- Ability to provide informed consent

Additional criteria for cohort A:

• Partner of a participating patient

Additional criteria for cohort B:

- Histological diagnosis of a solid malignancy
- Treatment with monotherapy immune checkpoint inhibitor (ICI) against Programmed Death 1 (PD1) or its ligand PD-L1 (in curative or non-curative setting)
- Last ICI administration within 3 months of vaccination

Additional criteria for cohort C:

- Histological diagnosis of a solid malignancy
- Treatment with cytotoxic chemotherapy (monotherapy and combination chemotherapy is allowed, as well as a combination with radiotherapy, in curative or non-curative setting)
- Last chemotherapy administration within 4 weeks of vaccination

Additional criteria for cohort D:

- Histological diagnosis of a solid malignancy
- Treatment with a PD1 or PD-L1 antibody in combination with cytotoxic chemotherapy (in curative or non-curative setting)
- Last chemotherapy administration within 4 weeks of vaccination
- Last ICI administration within 3 months of vaccination

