# 4.3 Exclusion criteria

A potential subject who meets any of the following criteria will be excluded from participation in this study:

- Confirmed SARS-CoV-2 infection (current or previous)
- Women who are pregnant or breastfeeding
- Active hematologic malignancy
- Any immune deficiency not related to cancer or cancer treatment (e.g. inherited immune deficiency or known infection with Human Immunodeficiency Virus)
- Systemic treatment with corticosteroids (> 10 mg daily prednisone equivalent) or other immunosuppressive medication within 14 days of vaccination. Inhaled or topical steroids, and adrenal replacement steroids (> 10 mg daily prednisone equivalent) are permitted. In addition, standard of care with short course steroids to prevent nausea and allergic reactions from chemotherapy or iodinated CT contrast is allowed.

Additional criteria for cohort A:

- Current or previous diagnosis of a solid malignancy, unless treated with curative intent >5 years before enrolment and without signs of recurrence during proper follow-up
- Previous history of a hematologic malignancy

Additional criteria for cohort B:

- Treatment with cytotoxic chemotherapy within 4 weeks of vaccination Additional criteria for cohort C:
  - Treatment with an ICI within 3 months of vaccination

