## Table 1: Flow chart/time and events schedule

Procedure	Screening a	Vacc	Vacc	Day	Day	Day	Vacc	Day	Day	Day	Day
	(within 28	1	2	28	90	180	3 m	28	270	330	540 (±
	days)			vacc	(±7)	(± 7)		vacc	(±7)	(± 14)	21)
				2 b				3			
				(± 3)				(± 3)			
Informed consent	х						х				
Inclusion/exclusion											
criteria	x										
Medical history	х										
Concomitant											
medication	x	х	х	х		X	x	х		x	X
Smoking history	х										
ECOG PS b	х										
Height/weight	х						х				
Vital signs c	х	х	х				х				
Blood tests d		х	х	х		х	х	х		х	х
Nasal MLF				х							
collection e		X									
Sollicited adverse				х							
events f	X	X	X				X				
SAEs g		х	х	х			x				
irAEs h	х	х	х	х			х	х			
AESIs i			Will be	e report	ed for t	he entii	re durat	ion of th	ne study		
Vaccine		~	~								
administration j		X	X				X				
COVID-19					~	~					
questionnaire k	X				X	X	X		x	x	x
Survival status						х				x	x

a Screening should be performed within 28 days prior to the first vaccination but can be done on the same day as the first vaccination.

b ECOG performance status: see appendix 3.

c Vital signs: blood pressure, heart rate, temperature.

d See Table 2.

e MLF = mucosal lining fluid, will be collected using a synthetic absorptive matrix [39] f Participants will complete a questionnaire for solicited systemic and local AEs on a daily basis from each vaccination until 7 days after each vaccination, see Appendix 1. g SAEs that occur within 7 days of each vaccination will be reported

h Newly developed irAEs [38] grade  $\geq$  3 need to be reported for cohort B and D up to 28 days after the second vaccination and from the third vaccination to 28 days thereafter.

i AESIs (see Appendix 2) will be reported by the treating physicians up to 18 months after vaccination for cohorts B-D.

j The name of the vaccine, batch number and date and time of administration will be recorded.

k Participants will complete a questionnaire for diagnosis of SARS-CoV-2 infection, severity and outcome of COVID-19.

 Only participants with an inadequate antibody response (≤300 BAU/mL) on day 28 after the second vaccination.

	Vacc1 a	Vacc2 a	Day	Day		Day		Day

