#### **10.2 Secondary study parameters**

- Incidence and severity of solicited AEs during 7 days after each vaccination is a key secondary endpoint (see Appendix 1). Frequencies and absolute numbers of mild, moderate and severe solicited AEs per cohort will be listed for the first, second and third vaccination separately.
- The numbers, nature and severity of SAEs graded according CTCAEv5.0 will be listed per cohort.
- Incidence and nature of newly occurring irAEs grade ≥ 3 in cohorts B and D up to 28 days after the second vaccination is the second safety endpoint. irAEs will be graded according CTCAEv5.0. Frequencies and absolute numbers of all newly occurring irAEs grade ≥ 3 that occur between the first vaccination and 28 days after the second vaccination in cohorts B and D will be listed.
- Incidence, nature and severity of AESIs comprise the third safety endpoint. AESIs will be graded according CTCAEv5.0. Absolute numbers and frequencies of all AESIs will be listed per cohort and subdivided by severity.
- Levels of SARS-CoV-2 S-specific IgG antibodies at 28 days after the second vaccination will be compared between each patient cohort and the non-cancer cohort using ANOVA or Kruskal–Wallis one-way analysis of variance, and Welch ttests or Mann-Whitney U tests, depending on the distribution of the data.
- Levels of SARS-CoV-2 S-specific IgG antibodies before the second vaccination and at 6, 11 and 18months after the second vaccination will be measured to assess early antibody response and longevity. GMCs and 95% CIs will be calculated. The absolute numbers and percentages of responders will be reported for each cohort for each time point. Antibody levels before the second vaccination and at 6, 11 and 18 months will be compared between each patient cohort and the non-cancer cohort using ANOVA or Kruskal–Wallis one-way analysis of variance, and Welch t-tests or Mann-Whitney U tests, depending on the distribution of the data.

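### irAE collection after the third vaccination follows a cohort label set at screening, not checkpoint-inhibitor exposure at that dose, so events in cohort C could be missed

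*Combined protocol and SAP*

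**What the plan says.** Section 3 states that "The patient cohorts are defined by type of cancer treatment". Section 4.2 gives the windows: "Last ICI administration within 3 months of vaccination" for cohorts B and D, and "Last chemotherapy administration within 4 weeks of vaccination" for cohorts C and D. Section 4.3 excludes from cohort C anyone with "Treatment with an ICI within 3 months of vaccination". None of these says which vaccination is meant. Table 1 marks the eligibility check at screening only, within 28 days before the first dose, so the label is in effect fixed there. No section re-checks or reassigns it later, and section 8.4.1 has no withdrawal criterion for a change of cancer treatment.

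For the third dose, section 3 says that newly occurring irAEs "are collected for the immunotherapy and chemo-immunotherapy cohorts (B and D) up to 28 days after the second and if applicable the third vaccination". Footnote h of Table 1 says that newly developed irAEs of grade 3 or higher "need to be reported for cohort B and D up to 28 days after the second vaccination and from the third vaccination to 28 days" after it. Sections 8.6 and 9.2.4 likewise tie irAE follow-up to cohorts B and D. In section 10.2, "solicited AEs per cohort will be listed for the first, second and third vaccination separately", and section 10.3 refers third-dose safety back to section 10.2. Sections 3 and 9.2.4 define irAEs as toxicities of checkpoint inhibitors.

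**The concern.** By the protocol's own definition, the people at risk of an irAE are those exposed to an ICI. At the first dose the cohort label is a good stand-in for that exposure, because the 3-month window has just been checked. At the third dose the label is months old and untested. Two errors are then possible. A cohort C patient who has started an ICI since enrolment receives the third dose with no irAE collection. A cohort B or D patient whose ICI has ended stays in a listing that is meant to describe patients on immunotherapy.

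At stake is how third-dose safety under checkpoint inhibition can be read. Section 1.4 names immune-related events as a specific worry with immunotherapy, so this is a question that the extension should be able to describe cleanly.

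**Working it through.** **1. Who is eligible for a third dose.** Inputs from section 1.6: evaluable patients B 131, C 229, D 143; adequate response 93.1%, 83.8%, 88.8%. The complements are 100 − 93.1 = 6.9%, 100 − 83.8 = 16.2% and 100 − 88.8 = 11.2%, which reproduce the figures in section 1.7.

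| Cohort | Calculation | Eligible | irAEs collected after dose 3 |
|---|---|---|---|
| B | 131 × 0.069 | 9 | yes |
| C | 229 × 0.162 | 37 | no |
| D | 143 × 0.112 | 16 | yes |
| All patients | 9 + 37 + 16 | 62 | 9 + 16 = 25 |

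The share in cohort C is 37/62 = 59.7%.

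**2. How old the label is at dose 3.** No day is stated. Three readings bound it.
- Eligibility needs the day-28 result after dose 2. Assuming 28 days between doses 1 and 2, the earliest date is 28 + 28 = 56 days after dose 1. That is past the 4-week chemotherapy window but not the 3-month ICI window.
- Table 1 places the third dose after the day-180 column. On the same assumption this is 180 + 28 = 208 days after dose 1: 208/28 = 7.4 times the chemotherapy window and 208/91.3 = 2.3 times the ICI window.
- Enrolment ran from 17 February to 12 March 2021 (section 1.6). Sections 1.8 and 13 point to autumn 2021. If dose 1 was at enrolment and dose 3 fell in September or October 2021, the gap is 173 to 256 days.

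**3. How many cohort C patients might be affected.** The documents give no switch rate, so this is an assumed range: 37 × 0.05 = 1.9, 37 × 0.10 = 3.7, 37 × 0.20 = 7.4, 37 × 0.30 = 11.1. That is about 2 to 11 patients if all 37 were dosed, and none if nobody switched.

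**4. What else would capture an irAE in cohort C.**
- SAEs are collected in every cohort, but for 7 days after each dose. irAE follow-up runs 28 days, so days 8 to 28 are not covered.
- AESIs are reported for cohorts B to D up to 18 months. The Appendix 2 list includes myocarditis, type I diabetes, acute aseptic arthritis, meningoencephalitis and death. It has no gastrointestinal or hepatic entry. Its open category depends on the treating physician seeing a relation to vaccination.

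A grade 3 or higher irAE on days 8 to 28 that is not on the list could therefore go unrecorded.

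**5. Where the irAE window ends.** Section 8.1.2 and section 9.2.4 run to 28 days after the last vaccination. The listing in section 10.2 stops 28 days after the second. Section 10.3 sends third-dose safety to section 10.2, which as written has no third-dose irAE listing.

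**The case against.** The best defence is that the third-dose aims are exploratory and descriptive (section 2), and that the question in section 1.7 is whether a further dose helps people who responded poorly to two. That poor response arose under the original treatment, so the original cohort is a legitimate way to group them. AESI and SAE reporting also reach cohort C, and concomitant medication is recorded at the third dose and 28 days after it, so exposure may be recoverable without any design change.

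Much of this stands. It justifies keeping the original cohort in the tables, and it keeps the point modest. It does not rescue the collection rule: an event that was never collected cannot be recovered by re-tabulating at analysis, and the plan does not say that the medication record covers anticancer drugs or will be used for this purpose.

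A reader might go further in three ways that the documents do not support.
- That irAEs were in fact missed. No cohort C patient is documented as having started an ICI.
- That third-dose antibody results by cohort are wrongly attributed to treatments that have ended. Section 10.3 describes that analysis for inadequate responders as one group and states no cohort split.
- That the irAE rate in B and D is diluted by a calculable factor. The share who stopped is not given, and any factor would rest on assuming no irAEs after the ICI stops.

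**Conclusion.** The rule is misaligned with the population at risk, and the point stands as a cheap improvement. After the third dose, irAE collection depends on a label set months earlier and never updated, so irAEs could be missed in a cohort C patient newly on an ICI, and the B and D listing may include patients no longer exposed. Per-cohort attribution is explicit for third-dose solicited AEs only.

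On size, cohort C holds about 60% of eligible patients. The 62 are eligible, not dosed: a third dose in the study needs separate consent (section 11.2), and others were invited through the national programme (section 1.8). Both the 37 and the 25 are therefore upper limits. The figure of 2 to 11 rests wholly on the assumed switch rate. The gap of months rests on column order and calendar dates, and the screening anchor on Table 1; neither is stated outright. The primary endpoint is not affected.

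**What to change.** - **Collection.** In footnote h, section 8.6 and section 9.2.4, with a matching sentence in section 10.2, keep cohorts B and D and extend third-dose irAE collection to any participant given an ICI from 3 months before the third vaccination to 28 days after it.
- **Identification.** Use the concomitant-medication record at the third vaccination and at day 28 after it. State that it covers anticancer drugs, with dates, and that it looks back over the windows in section 4.2.
- **Listing.** Show third-dose irAEs and AEs descriptively by current treatment status beside the original cohort, without tests.
- **Reconciliation.** Bring the end of the irAE listing in section 10.2 into line with sections 8.1.2 and 9.2.4, so that a third-dose irAE listing exists.

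The cost is one derived variable, a few sentences, and chart retrieval for a few cohort C patients. The subgroups by current treatment will be small and can only be described.
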